- Cognitive impairment (documented in medical record and/or MIS-T score of less than 4);
- ACT therapy within the past year;
- Inability to attend workshop prior to surgery;
- Imminent risk of suicide (including recent, related hospitalization);
- Indicated surgery is revision of TKA

Termination

Participants will be terminated from the study if they do not have surgery within approximately one year of attending workshop

Re-approaching Potential Participants

Consented participants who do NOT meet inclusion criteria before their surgery may be rescreened, re-approached, re-consented and reassessed for eligibility if they are indicated to have a second TKA surgery before the end of the study enrollment period. These participants will be eligible for this reassessment no earlier than eight weeks after their first TKA.

Data Analysis

Descriptive statistics (means, medians, percentages, standard deviations, and inter-quartile ranges) of all variables will be computed for each intervention group. We will describe sex and race/ethnicity results separately to identify potential differences, based on these biological variables. The distributions of continuous variables will be evaluated for normality. If data are non-normal, statistical analyses appropriate for non-normal data will be utilized (see below). Variables will be compared across intervention groups using a t-test for continuous variables, Wilcoxon-rank sum test for ordinal and non-normally distributed continuous variables, and Pearson Chi-square test for categorical variables. Variables that are found to significantly differ between the groups will be used as covariates in the comparison of outcome measures between the treatment groups.

Intent-to-treat (ITT) analyses will be conducted to assess treatment efficacy on post-operative outcomes using all subjects that have been randomized and had surgery performed. Only those who receive surgery are included in these analyses to test the efficacy of ACT on the primary and secondary outcome measures because our underlying model for treatment effectiveness is based on the assumption that ACT will prevent the development of PPSP by helping Veterans cope with postoperative pain. Therefore, receipt of surgery is inherent in our treatment model. Follow-up data on randomized subjects that did not have surgery will be included in a secondary analyses that will contrast the effect of ACT between those with and without surgery.

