For the secondary aim (B), mediation analysis will explore the causal pathway between intervention (ACT or AC) and change in pain intensity and functioning from baseline to 6 months with decreases in anxiety and depressive symptoms, and increases in acceptance-based coping and engagement in values-based behaviors from baseline to 6 weeks, and baseline to 3 months as mediators. With the independent variable X (intervention) randomized to workshops (clusters), and the mediator variables M (decreases in anxiety and depressive symptoms and increases in acceptance-based coping and engagement in values-based behaviors), and the dependent variable Y (changes in pain & function) measured at the subject level within clusters, we have a two-level hierarchy with a 2-1-1 design. For this multilevel design, multilevel structural equation modeling (MSEM) will be used to estimate and test the direct and indirect effects to assess multilevel mediation as described by Preacher, Zyphur, and Zhang¹⁰⁵ using SEM in Stata.

In the case of subject drop-out, reasons for subject drop-out will be recorded and compared between treatment groups. Subject characteristics and outcome measures collected prior to drop-out for those that drop out post-surgery will be compared to those that complete the study. In the presence of missing data, under the assumption of missing at random (MAR), linear mixed model analysis which can handle incompletely observed subjects and uses a likelihood estimation method will provide correct likelihoods and lead to valid estimates.¹⁰⁶ Similarly, the use of the weighted GEE method is able to handle missing responses caused by dropouts in a longitudinal study.¹⁰⁷ However, since the data under analysis cannot distinguish if data is MAR or it is missing not at random (MNAR), sensitivity analysis will also be performed using pattern mixture models. Multiple imputation will be used for sensitivity analysis by imputing from a non-random pattern mixture model.¹⁰⁸

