For the exploratory aim, frequencies for each pharmacologic and non-pharmacologic pain management strategy will be calculated to describe the types of strategies reported at each visit. Patterns (from baseline to 6 months) and trends (i.e. changes over the 4 year data collection period) will be examined. Helpfulness ratings will be averaged using means and standard deviations or medians and interquartile ranges for each strategy to provide insights on strategies at-risk Veterans find helpful. Differences in types and helpfulness of pain management strategies by treatment group will be explored.

Sample Size

Sample size was estimated using KOOS-Activities of Daily Living Subscale (the primary outcome requiring the largest sample size). According to the literature, a change of 8 points or more represents a clinically significant improvement.⁸⁵ Therefore, assuming an average of 6 participants per workshop (cluster), with an ICC of 0.06 and a standard deviation of 18, a sample size of 300 Veterans (n=150 per treatment group) will be needed to detect a clinically

significant difference of 8 at a 0.0167 significance level (adjusted for testing at 3 time points) with 0.80 power. Assuming 20% will have surgery cancelled/postponed due to health issues and 10% will drop out after randomization (17% and 10%, respectively, was observed in our R34 study), we plan to enroll 430 Veterans to ensure that we will have $n=150$ per treatment group for the primary aim analyses. Veterans who do not have surgery after randomization will be followed over a similar timeframe and will be included in the secondary analyses.

Recruitment, Consent and Enrollment

Summary of recruitment and consent process, in-person

Identifying Patients

In order to increase awareness of the study, flyers describing the study will be posted in the orthopedics clinic and copies will be made available for patients to take. The study's Research Assistant (RA) will use Vista to identify all patients scheduled in the VAMC Orthopedics Clinic for a knee pain consultation. The RA will then review these patients' medical records to determine if they speak English with adequate competence AND do not have a diagnosis of dementia, bipolar or psychotic disorder, or history of brain injury. They will also review prior orthopedic notes to gauge readiness for surgery.

Approaching Patients

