This study will use a cluster randomization approach where the unit of randomization will be the workshops. Randomization will occur right before each workshop so that all participants attending that workshop will be randomized to that intervention (i.e. ACT vs. AC). Statistician [name] will generate the randomization sequence to ensure adequate distribution of the two interventions over the study period. Randomization will be stratified by site (i.e. Iowa City versus Houston). The randomization sequence will be maintained by the Statistician in a password protected file. This file will be used to generate concealed envelopes maintained and accessed by a facilitator at each site. Allocation of workshop to intervention group will remain concealed for facilitators until approximately one week before the workshop to allow for the needed preparation. Workshop allocation to intervention group will remain concealed for all other study personnel and participants until the beginning of the workshop when all invited participants have arrived. Those in attendance will receive the assigned intervention. This allocation approach will eliminate pre-treatment withdrawals, minimize the potential for experimenter and participant bias by protecting the randomization sequence in a central location, maintain concealment of treatment allocation until the last possible moment, and keep the participants and outcome assessors blinded to treatment.

Virtual Workshops

The randomization scheme for BCM should be used for all virtual workshops.

Blinding

This is a double-blind study. Participants are blinded to which treatment is the treatment of interest and outcome assessors will be blinded to which treatment participants receive. The treatment allocators (i.e. project coordinators) and the workshop facilitators will not be blinded so they can be available throughout the study to answer questions regarding treatment. It is essential for them to know which group the participant is in, in case they need to troubleshoot the treatment.

Participants will complete the Workshop Usefulness Survey (Workshop Question 6wk) in REDCap at the end of their 6-week assessments and the Participant Blinding Question in REDCap at the end of their 6-month assessment. Assessors will complete the Assessor Blinding Question (Workshop Question 6mo) in REDCap at the end of each participants' 6-month assessment.

Post-Op Evaluations

6 Weeks, 3 Months and 6 Months Post-Op Surveys

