At 6 weeks, 3 months and 6 months postop, all Veterans will receive REDCap automated survey invitations and, if they have consented to participate in the Department of Veterans Affairs' Annie mobile Short Message Service (SMS) text messaging, short text messages reminding them to take the survey. If participants prefer, paper copies of these surveys will be mailed to them with a cover letter. At 6 weeks, the survey will include: BPI; DASS-21; PCS; OQ-45.2; KOOS - postop; CPAQ; CPVI; Promise Sleep; Complications; and workshop usefulness (6wk). At 3 months, the survey will include: BPI; DASS-21; PCS; PMSS (postop); OQ-45.2; KOOS - postop; CPAQ; CPVI; and Promise Sleep. At 6 months, the survey will include: BPI; DASS-21; PCS; PMSS (postop); OQ-45.2; KOO - postop; CPAQ; CPVI; Promise Sleep; Workshop Usefulness (6mo); and COVID-19 Impact.

Survey Review

In each case, after the participant has completed the surveys, the RAs will cross-check the medications reported in the BPI and DASS-21 with those in the medical record and discuss discrepancies with the participant.

Data Collection and Quality Assurance

Data management

The Study Coordinator at the Coordinating Site will be responsible for:

1. Designing and maintaining the REDCap data collection site as well as the Tracking Database
2. Ensure all data is stored so that blinded study personnel do not have access to any data that would un-blind them.
3. Conduct regularly scheduled audits (including hard-copy-to-electronic-copy checks) and data quality checks

REDCap

All data collection forms will be available through a REDCap (Research Electronic Data Capture) database (supported by the institutional CTSA) and patients can directly enter data into these forms. They will enter data into a central database through their computer or a tablet provided in the clinic. This will eliminate error in data entry, and reduce time necessary for data entry, cleaning and analysis. Range checks will be programmed into the data entry system when the nature of the data allows so that it will not permit invalid values to be entered into the database.

When a data collection session is completed, the RA will review electronic forms for completeness and validity. The RA will resolve all queries and will enter an override for all values that have been confirmed as being accurate. Reports will also be run periodically to confirm or correct questionable values. All changes will be tracked through the REDCap audit trail.

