Upon enrollment, all participants will be provided with the phone number of the local VAMC's Suicide Prevention Coordinator as well as the Veteran crisis hotline. If at any time during participation in study assessments, the workshop or "booster" session a participant indicates suicidal ideation, a research team member will ask 3 follow-up questions as indicated by the Suicide Risk Protocol. If these follow up questions suggest that suicide is imminent (i.e., the participant answers 'yes' or 'maybe' to question 3 of the Suicide Risk Assessment or describes a detailed plan to kill him/herself on a specific date in the immediate future), emergency services will be utilized as per the protocol detailed in the "Suicide Risk Management" document. In addition, patients with imminent risk of suicide, attempts of suicide, incidents of violence toward others, or psychiatric hospitalizations will lead to withdrawal from the research protocol and will be reported to the SMC, institutional IRB and NINR.

Protecting Confidentiality of Participant Data

A number of precautions will be undertaken in order to protect the confidentiality of study participants. All documents containing identifying information (e.g. consent forms, patient correspondence) will be kept separate from the participant's main data file at each site. The main data file will contain only study identifier numbers. A separate key that links the two sets of files will be kept by the study coordinator in a separate locked file. All data will be locked in the research offices of the PIs and study site coordinators. The PIs will have a shared electronic folder in order to share information. Only the PIs and key research staff will have access to this electronic folder. The computers on which data are entered will also be kept in the locked research offices; access to the computers is password-protected. Computer data will be entered by subject code only (without identifying information). The codes will be kept in a locked safe or a password-protected database, in an encrypted computer behind the VA firewall. No subject will be identified by name in any report of the study. Data will be kept confidential and will not be released to the general public. Data will be available to research staff, institutional IRB's and government agencies as required.

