The project coordinator in conjunction with the steering committee will determine when data collection is complete based on when the anticipated number of participants in each study group have been completed (ACT, AC). A final decision on data collection will be initiated by the study coordinator and brought to the steering committee for final approval. This will be based on achieving an adequate number of subjects per group (150 per group) who have completed all data collection.

Upon completion of the study, the project coordinator and the primary investigators at University of Iowa and Baylor University will notify the appropriate IRB at each institution, the study team, SMC, NINR, and clinical trials.gov of trial completion. This will involve a modification to the IRB, and a written letter to the study team, SMC, NINR and changing the status on clinical trials.gov online.

Study files will be archived and stored in the study's shared file on the VA server and in the study's file on the University of Iowa server. These will then be made available as needed for external audits.

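### The safety-withdrawal rule does not separate stopping study sessions from stopping outcome surveys, so scores after a serious psychiatric event may go uncollected

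*Combined protocol and SAP*

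**What the plan says.** The rule is in the Data and Safety Monitoring Plan, under Minimizing Risk Associated with Suicidal Ideation and Psychological Distress. After the emergency steps for suicidal ideation, it lists four triggers: imminent suicide risk, suicide attempt, violence toward others and psychiatric hospitalization. It ends: "psychiatric hospitalizations will lead to withdrawal from the research protocol and will be reported to the SMC, institutional IRB and NINR". Suicidal ideation may come to light at an assessment, at the workshop or in a booster call, so a trigger can arise after randomization and after surgery.

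Other sections bear on what withdrawal means for the data:

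- **Post-Op Evaluations:** at each of the three follow-up times "all Veterans will receive REDCap automated survey invitations". Withdrawn Veterans are not mentioned.
- **Data Analysis:** the intent-to-treat set is everyone randomized who had surgery. On drop-out, "reasons for subject drop-out will be recorded and compared between treatment groups", and outcomes gathered before drop-out are compared with those of completers. The main model is a likelihood-based mixed model under missing at random, and "sensitivity analysis will also be performed using pattern mixture models".
- **Sample Size:** continued follow-up is promised to one off-plan group only, Veterans who are randomized but do not have surgery.
- **Study Completion and Closeout Procedures:** the decision to end data collection rests on "achieving an adequate number of subjects per group (150 per group) who have completed all data collection".

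**The concern.** Stopping an intervention and stopping measurement are different decisions, and the rule makes both with one word. If withdrawal ends the surveys, the trial loses scores from Veterans selected by a severe psychiatric event. Most of the triggers are extreme states of the distress that DASS-21 measures; violence toward others is less directly so. Anxiety and depressive symptoms are secondary outcomes, and their changes to 6 weeks and 3 months are planned mediators. The missing scores would therefore probably differ from what earlier scores predict, which is the situation a missing-at-random model handles least well.

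At stake are the contrast between arms, if events differ by arm in frequency or severity, and otherwise the record of how these Veterans fared after the event. The loss would be avoidable, because the surveys and the means of sending them already exist.

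**Working it through.** **Step 1. Does the text end survey collection?** No section says so, and none says the opposite. Three things favour the reading that collection ends.

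- The first booster is two weeks after surgery. A conditional second booster is tied mainly to the 6-week assessment window. For an event found at the 3-month survey, little remains to withdraw from except the 6-month survey.
- Continued follow-up is written out for Veterans without surgery and not for this group.
- The drop-out text refers only to outcomes gathered before drop-out.

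The survey-schedule sentence covers all Veterans, but it is a general schedule and does not override a specific withdrawal rule.

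**Step 2. Who is affected?**

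- Imminent suicide risk is an exclusion criterion, so events should be few.
- Events before the workshop cost no randomized Veteran: "Workshop allocation to intervention group will remain concealed for all other study personnel and participants until the beginning of the workshop".
- An event that surfaces at a completed 6-month survey costs no scheduled score.
- An event between workshop and surgery, if surgery goes ahead, could cost all three surveys while the Veteran remains in the analysis set.

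**Step 3. The plan's own figures.** Inputs from Sample Size: difference 8, SD 18, alpha 0.0167 (taken as two-sided), power 0.80, 6 per workshop, ICC 0.06.

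- Design effect = 1 + (6 − 1) × 0.06 = 1.3.
- The normal approximation gives 106 per arm, and 106 × 1.3 = 137.8.
- A cluster-level t calculation with 2(k − 1) degrees of freedom gives power 0.791 at k = 24 workshops per arm (144 Veterans) and 0.811 at k = 25 (150). This reproduces the stated 150 per group.
- Enrolment: 300 / (1 − 0.20 − 0.10) = 428.6, stated as 430.
- Planned standard error of the KOOS-ADL contrast = 18 × √(2 × 1.3 / 150) = 2.37.

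**Step 4. Possible loss of data.** The documents give no event rate, so 0.5% to 3% of 300 is assumed.

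- Veterans: 0.005 × 300 = 1.5 to 0.03 × 300 = 9.
- Surveys: at most 9 × 3 = 27 of 300 × 3 = 900, or 3%.

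**Step 5. Possible shift in the contrast.** Let p be the share of an arm with an event before the visit analysed, and e the amount by which those Veterans' unseen scores are worse than the rest of their arm. If they are treated as resembling the rest of the arm, the contrast moves by pA × eA − pB × eB.

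Assumed ranges are an arm difference in rate of 0 to 2 percentage points, e of 10 to 25 DASS depression points, and e of 9 to 18 KOOS-ADL points (half to one planning SD).

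| Scenario | DASS depression | KOOS-ADL |
|---|---|---|
| Rates and severity equal | 0 | 0 |
| Rates differ by 2 points, severity equal | 0.02 × 25 = 0.50 | 0.02 × 18 = 0.36 |
| Rates equal at 3%, severity differs | 0.03 × (25 − 10) = 0.45 | 0.03 × (18 − 9) = 0.27 |
| Both differ, arms at 4% and 2% | 0.04 × 25 − 0.02 × 10 = 0.80 | 0.04 × 18 − 0.02 × 9 = 0.54 |

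The last row is the largest value these ranges allow: a pooled 3% with a 2-point difference is 4% against 2%, that is 6 and 3 Veterans of 150. For KOOS-ADL, 0.54 / 8 = 6.75% of the target difference and 0.54 / 2.37 = 0.23 of the standard error. If only half the events precede the visit analysed, these shifts halve (for example, 0.50 becomes 0.25). Pre-event scores in the mixed model would shrink them further.

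**The case against.** The strongest reply is that the end of surveys is inferred from silence. The sentence is a participant-safety rule, not a data rule. It sits beside references to a Suicide Risk Protocol and a Suicide Risk Management document, and the protocol also relies on a common Manual of Operations. Those documents and the consent form, none of them available here, are where instructions on contact after an event would normally be found. This stands, and it is why the point is put as the most natural reading and not as an established fact. A reader might infer that the protocol orders surveys to stop; it does not.

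Second, withdrawing someone after a suicide attempt is a defensible clinical choice, and any exit for clinically inadvisable contact would apply most to the sickest Veterans. That also stands: recovery would be partial. It does not explain why a Veteran who is willing and well enough should go unsurveyed.

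Third, the analysis plan already handles much of the consequence. A reader might infer that these Veterans leave the intent-to-treat set. They do not: an operated, randomized Veteran stays in it, with pre-event scores in the model. Drop-out reasons are compared by arm, and the pattern-mixture analysis addresses data missing not at random. What remains is that this analysis has to assume scores that could have been observed.

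Fourth, a reader might infer a loss of power. The sample size already assumes that "10% will drop out after randomization", and data collection closes on a count of completers. That protects the number of scores, though not the scores of these Veterans.

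**Conclusion.** The point holds as a gap in the withdrawal rule with a probably small effect, worth a low-cost change. As written, the rule most naturally ends outcome collection for a few Veterans selected by severe distress who remain in the intent-to-treat set, and nothing in the public documents restores their follow-up.

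The contrast is biased only if event rates or severity differ by arm, and nothing in the documents shows that they will. Equal rates cannot be taken for granted either, because unblinded facilitators can detect events at the workshop or booster and the two workshops differ in content. The direction cannot be known in advance, so inferring that the rule favours one arm would go beyond the documents. If rate and severity are equal, only information on these Veterans' later course is lost.

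The figures rest wholly on assumed rates and severities and are illustrations, not estimates. Even their upper end is under a quarter of a standard error on KOOS-ADL. Confidence is medium, because the unseen operational documents could already settle the matter.

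**What to change.** Amend the rule to say, in substance: these events stop further study sessions as clinically indicated; the scheduled 6-week, 3-month and 6-month surveys continue unless the Veteran withdraws consent or contact is judged clinically inadvisable. Keep the emergency steps and the reporting to the SMC, IRB and NINR unchanged. Add a sentence to the missing-data text in Data Analysis stating that scores collected after such an event are used in the intent-to-treat analysis.

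The cost is a short protocol amendment with IRB review, plus a consent amendment only if the consent form says otherwise. No new instrument, procedure or sample size is needed. The downside is sensitive re-contact after a serious event. Some Veterans will refuse or should not be approached, so only part of the missing scores will be recovered.
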